## 7.6 Unscheduled Visit

Should an unscheduled visit occur, it would likely be due to an adverse event. At this visit, the study subject will be assessed as standard of care. Recording of SAEs or AEs will be done according to Section 9 of this protocol.

---

## 8 STUDY PROCEDURES/EVALUATIONS

The study procedures and evaluations are summarized in Appendix B. Allowable windows for each study visit have been described previously. Some assessments and medical history information may be collected from the subject's medical charts as outlined below.

### 8.1 Clinical Evaluations

#### 8.1.1 Baseline Demographics

Data collected will include basic demographics and selected laboratory parameters. The following information will be collected from the subjects medical records to the extent the information is available: date of birth; gender; race; ethnicity; birth weight; length at birth, if available; head circumference at birth, if available; gestational age at birth; medical history and baseline conditions prior to study enrollment, by body system.

#### 8.1.2 Growth Parameters

To adjust study medication for weight gain, weight will be recorded at multiple study visits. To assess additional growth parameters, length and head circumference will be recorded at multiple study visits.

#### 8.1.3 Adverse Event Assessment

At each study visit from the receipt of first dose of study drug and continuing through four weeks following the final dose of study drug, the study subject will be assessed for any adverse events.

#### 8.1.4 Hearing Assessment

During the Screening Period (window:  $\leq 30$  days of age) and at Study Month 4 (window: -10 to +30 days), Study Month 6 (window: -10 to +30 days), Study Month 12 (window: -10 to +30 days), and Study Month 18 (window: -10 to +30 days), age-appropriate assessments of hearing will be performed. Results of hearing assessments conducted for clinical care may be utilized if conducted within the study window. BSER and/or visual reinforcement audiometry (VRA) (to assess neuro-otologic status) and OAEs (DPOAE or TEOAE) will be obtained. If the BSER and/or VRA is abnormal, then bone conduction will be obtained to distinguish between sensorineural hearing loss, conductive loss, or mixed loss. If the OAEs are abnormal, then acoustic immittance measures (tympanometry and acoustic reflexes) will be obtained to better define the middle or inner ear abnormality (e.g., otitis media).

If a study subject proceeds to cochlear implantation during the course of the study, he/she will not require additional study-related hearing assessments following the implantation procedure but will continue with all other study-related assessments. Prior to the implantation, efforts will be made to obtain audiology testing that would have been performed at the Month 6 visit.

---

## 8.2 Laboratory Evaluations

Blood for study-specified laboratory evaluations may be obtained by methods such as the following: venipuncture, heel stick, indwelling heparin- or saline-locked intravenous catheter, etc. As detailed below, blood will be obtained for assessment of hematology safety labs, chemistry safety labs, and whole blood CMV virology studies. If an insufficient volume of blood is obtained for all of the tests at any given study visit, the following prioritization as to which tests to send will apply (most important to least important): 1) hematology safety labs (most important); 2) chemistry safety labs (second most important); and 3) whole blood CMV virology studies (third most important). With the exception of the hematology safety labs and ALT assessments, those lab tests which are unable to be obtained due to lack of sufficient blood or parental refusal at a given study visit will be noted but will not be reported as protocol deviations.

If possible, urine collection by bagged or clean catch specimen will be attempted at designated study visits (Study Day 1, and Months 4, 5, and 6). Inability to collect urine will be documented but not reported as a protocol deviation. Saliva will be collected using polyester fiber-tipped swabs at each of these designated study visits as well. Specimens will be shipped to the UAB Central Laboratory for analysis.

As far as possible safety labs and other research specimens should be taken to coincide with clinical care. If it is not possible to obtain samples for safety labs at a study visit and bloods were obtained for clinical care within 2 days of the study visit, the data may be extracted from the medical records.

### 8.2.1 Clinical Laboratory Evaluations

The breakdowns of the amount of blood for individual tests are provided in Appendix B. Clinical laboratory results can be used for chemistry and hematology safety labs if collected for clinical care and within the required study window. If labs drawn for the study required assessments are not evaluable, blood draws will not be repeated.

#### 8.2.1.1. Hematology Safety Labs

All hematology safety laboratory assessments will be conducted at the PI's local lab. These assessments will provide information on the safety of administering the study drug. They will be obtained weekly for the first six weeks of study drug administration, then every other week for the next six weeks of study drug administration, and then at months 4 and 5. The following will be tested: white blood cell count, differential, hemoglobin, and platelet count.

#### 8.2.1.2. Chemistry Safety Labs

All chemistry safety laboratory assessments will be conducted at the PI's local lab. These assessments will provide information on the safety of administering the study drug. They will be obtained every other week for the first 12 weeks (3 months) of treatment, and then at months 4, 5, and 6. The following will be tested: ALT, direct bilirubin, and creatinine.

## **8.2.2 Special Assays or Procedures**

### **8.2.2.1 CMV Virologic Testing**

Assessment of CMV viral load by quantitative PCR will be conducted at the UAB Central Laboratory. In study subjects with increasing whole blood viral loads during the course of treatment, assessment for antiviral resistance may be undertaken on the serially collected samples.

Antiviral resistance will be performed in the UAB Viral Resistance Laboratory.

## **8.2.3 Specimen Preparation, Handling, and Shipping**

### **8.2.3.1 Instructions for Specimen Preparation, Handling, and Storage**

Specific instructions on specimen collection, preparation, handling, and storage will be provided in the Manual of Procedures for this study.

### **8.2.3.2 Specimen Shipment**

Specific instructions on specimen shipping will be provided in the Manual of Procedures for this study.

---

## 9 ASSESSMENT OF SAFETY

Regulatory requirements including the Food and Drug Administration (FDA) regulations, International Conference on Harmonisation (ICH) Guidelines for Good Clinical Practice (GCP), and European Union (EU) Clinical Trials Directive set forth safety monitoring and reporting responsibilities of sponsors and investigators to ensure the safety and protection of human subjects participating in clinical trials.

### 9.1 Specification of Safety Parameters

An Adverse Event is any unfavorable and unintended sign (including an abnormal laboratory finding), symptom, or disease temporally associated with the use of medicinal (investigational) product whether or not considered drug related. The occurrence of an AE may come to the attention of study personnel during study visits and interviews of a study recipient presenting for medical care, or upon review by a study monitor.

Investigators participating in this clinical trial are responsible for and will:

- Evaluate subject safety including assessment of adverse events (AEs) for seriousness, severity, and causality;
- Notify the Central Unit, CROMS PVG, and EMMES of protocol-defined serious adverse events (SAEs) within 24 hours; (details provided in the MOP)
- Provide detailed written reports, including necessary documentation requested by the sponsor or institutional review board (IRB)/independent ethics committee (IEC), promptly following immediate initial reports; and
- Inform the IRB/IEC of AEs as required by applicable regulatory requirements.

### 9.2 Methods and Timing for Assessing, Recording, and Analyzing Safety Parameters

#### 9.2.1 Adverse Events

Information to be collected on reportable AEs includes event description, time of onset, clinician's assessment of severity, relationship to study product (assessed only by those with the training and authority to make a diagnosis, which would include MD or DO), and time of resolution/stabilization of the event. All AEs occurring from Study Day 1 through four weeks following the last dose of study drug must be documented appropriately regardless of relationship. All AEs will be followed to adequate resolution. SAE reporting is described in section 9.2.2.

Any medical condition that is present at the time that the patient is randomized should be considered as a baseline condition and not reported as an AE. However, if the event meets the criteria in Section 9.2.1 and the grade of the event worsens at any time during the study, it should be recorded as an AE.

The determination of seriousness, severity, and causality will be made by an on-site investigator who is qualified (licensed) to diagnose AE information, provide a medical evaluation of AEs, and classify AEs based upon medical judgment. This includes MD or DO. Events will be identified by assessing the subject at each visit. If a subject is hospitalized, the medical record should be reviewed to identify AEs. The PI is responsible for identifying and reporting AEs according to protocol guidelines.

**Severity of Event:** All reportable AEs will be graded by the investigator according to the protocol toxicity tables (Appendix A) using a four-grade system (Table 2). For safety laboratory results with an absolute number in the toxicity tables (e.g., hemoglobin), grading of the AEs will be according to the toxicity tables and not according to the local laboratory reference range. For safety laboratory results with a reference to the Upper Limit Normal (ULN) in the toxicity tables (e.g., AST or SGOT), grading of the AEs will utilize the ULN of the local laboratory reference range in determining grading of the event per the toxicity tables. Grade 4 AEs will be only reported as SAE if the event meets one of the regulatory definitions of SAE described below (9.2.2) based on the study site physician judgment. The functional table below should be used to grade the severity of an AE that is not specifically identified in the grading table. In addition, all deaths related to an AE are to be classified as grade 5.

Table 2. Four-grade system utilized for this trial (see also Appendix A)

PARAMETER	GRADE 1 MILD	GRADE 2 MODERATE	GRADE 3 SEVERE	GRADE 4 POTENTIALLY LIFE- THREATENING
Clinical adverse event NOT identified elsewhere in the grading table	Mild symptoms causing no or minimal interference with usual social & functional activities with intervention not indicated	Moderate symptoms causing greater than minimal interference with usual social & functional activities with intervention indicated	Severe symptoms causing inability to perform usual social & functional activities with intervention or hospitalization indicated	Potentially life-threatening symptoms causing inability to perform basic self-care functions with intervention indicated to prevent permanent impairment, persistent disability, or death

The severity of the events will be mapped to a 3 Grade system for reporting events to the FDA, in accordance with CDISC standards. The four-grade system allows direct comparisons to previous studies. The investigators and the data coordinating center will develop the mapping algorithm to collapse the 4 grades that allow for comparison across studies down to the 3 grades needed to meet CDISC standards.

---

### 9.2.2 Serious Adverse Events

Event seriousness will be determined according to the protocol definition of an SAE.

An adverse event or suspected adverse reaction is considered “serious” (will be an SAE) if, in the view of either the investigator or sponsor, it results in any of the following outcomes:

- Death,
- a life-threatening adverse event\*,
- inpatient hospitalization or prolongation of existing hospitalization,
- a persistent or significant incapacity or substantial disruption of the ability to conduct normal life functions, or
- a congenital anomaly/birth defect.
- Important medical events that may not result in death, be life-threatening, or require hospitalizations may be considered serious when, based upon appropriate medical judgment they may jeopardize the patient or subject and may require medical or surgical intervention to prevent one of the outcomes listed in this definition. Examples of such medical events include allergic bronchospasm requiring intensive treatment in an emergency room or at home, blood dyscrasias or convulsions that do not result in inpatient hospitalization, or the development of drug dependency or drug abuse.

\* Life-threatening adverse event. An adverse event is considered “life-threatening” if, in the view of either the investigator or sponsor, its occurrence places the patient or subject at immediate risk of death. It does not include an adverse event that, had it occurred in a more severe form, might have caused death. It does not necessarily include all grade 4 AEs according to the toxicity tables in Appendix A.

Events related to cochlear implantation will be recorded on the CRF, but will not be considered an AE or SAE unless meeting one or more of the above outcomes.

All SAEs will be:

- recorded on the appropriate SAE eCRF
- followed through resolution or stabilization by a study physician
- reviewed and evaluated by a study physician

Relationship to Study Products: The physician’s assessment of an AE's relationship to valganciclovir study drug is part of the documentation process, but it is not a factor in determining what is or is not reported in the study. If there is any doubt as to whether a clinical observation is an AE, the event should be reported. All AEs must have their relationship to study product assessed using the terms “related” or “not related,” and should be followed through resolution or stabilization. In a clinical trial, the study product must always be suspect.

The investigator must provide an assessment of relationship of AEs to the study product based on:

- 
- Temporal relationship of the event to the administration of study product;
  - Whether an alternative etiology has been identified;
  - Biological plausibility; and
  - Existing therapy, and/or concomitant medications.

To help assess, the following guidelines are used:

- Related– There is a reasonable possibility that the study product caused the adverse event. Reasonable possibility means that there is evidence to suggest a causal relationship between the study product and the adverse event.
- Not Related– There is **not** a reasonable possibility that the administration of the study product caused the event.

### **9.2.3 Procedures to be Followed in the Event of Abnormal Laboratory Test Values or Abnormal Clinical Findings**

If baseline clinical labs performed on Study Day 1 fall within Grade 1 abnormalities, then a laboratory AE is reported only if the value changes such that it falls into Grade 2 or higher at subsequent visits. For laboratory results that are abnormal according to the local laboratory reference range but not considered a Grade 1 abnormality, these will not be recorded as AEs.

Laboratory parameters other than those specified in sections 8.2.1.1 (hematology safety labs) and 8.2.1.2 (chemistry safety labs) as part of the CBC and complete metabolic panel need to be evaluated by the site physician, recorded in the source document, and reported as laboratory AEs if clinically significant.

## **9.3 Reporting Procedures**

### **9.3.1 Serious Adverse Events**

When a site identifies any SAE that meets the protocol-defined serious criterion, a call will first be made to the Clinical Studies Administrator at the Central Unit. Within 24 hours of identification, the SAE will be entered into the eCRF and the original signed SAE document will

---

be faxed to the Central Unit. If a signature from the PI is not obtained within 24 hours, it will be faxed without the signature.

[contact] to the attention of Central Unit Safety Coordinator.

The Central Unit will report all serious adverse events to DMID pharmacovigilance contractor, at the following email address: SAE Email address - [contact].

Should it be necessary for the Central Unit to contact the DMID Pharmacovigilance Group the following is contact information:

DMID Pharmacovigilance Group  
Clinical Research Operations and Management Support (CROMS)  
[name]  
[name]  
SAE Hot Line: [name] (US) or [name] (outside US)  
SAE FAX [contact] (US) or [name] (outside US)

Other supporting documentation of the event may be requested by the DMID pharmacovigilance contractor and should be provided as soon as possible. The DMID pharmacovigilance contractor will notify the DMID medical monitor and clinical protocol manager. The DMID medical monitor will review and assess the SAE for regulatory reporting and potential impact on study subject safety and protocol conduct. At any time after completion of the study, if the investigator becomes aware of an SAE that is suspected to be related to study product, the investigator will report the event to the DMID Pharmacovigilance Group.

### **9.3.2 Regulatory Reporting for Studies Conducted Under DMID-Sponsored IND**

Following notification from the Central Unit, DMID, the IND sponsor, will report to FDA any suspected adverse reaction that is both serious and unexpected. DMID will report an adverse event as a suspected adverse reaction only if there is evidence to suggest a causal relationship between the drug and the adverse event. DMID will notify FDA and all participating investigators (i.e., all investigators to whom the sponsor is providing drug under its INDs or under any investigator's IND) and the Central Unit in an IND safety report of potential serious risks from clinical trials or any other source, as soon as possible, but in no case later than 15 calendar days after the sponsor determines that the information qualifies for reporting as specified in 21 CFR Part 312.32. DMID will also notify FDA of any unexpected fatal or life-threatening suspected adverse reaction as soon as possible but in no case later than 7 calendar days after the sponsor's initial receipt of the information. Relevant follow-up information to an IND safety report will be submitted as soon as the information is available. Upon request from

---

FDA, DMID will submit to FDA any additional data or information that the agency deems necessary, as soon as possible, but in no case later than 15 calendar days after receiving the request.

All serious events designated as “not related” to study product(s), will be reported by DMID to the FDA at least annually in a summary format.

The Site Investigator is responsible for informing the Ethics Committee and/or IRB of the SAE as per local requirements. For non-US sites, the site investigator is responsible for also informing their Regulatory Authority as required by their local regulations.

### **9.3.3 Other Adverse Events (if applicable)**

In earlier investigations of ganciclovir and valganciclovir in infants, the side effect that was seen commonly was neutropenia. Therefore, neutropenia occurring during the course of the treatment period of the study will be assumed to be associated with study medication. The study site will notify the Statistical and Data Coordinating Center within 24 hours of identification of the following safety laboratory AEs:

- Any absolute neutrophil count (ANC) < 500 cells/mm^3
- Any platelet count < 50,000/mm^3
- Any ALT value ≥ 5-times the baseline value

## **9.4 Type and Duration of Follow-up of Subjects after Adverse Events**

Document all AEs, including safety laboratory AEs, from Study Day 1 through four weeks following the last dose of study drug. Document all SAEs from Study Day 1 through one month after completion of study medication.

All AEs and SAEs will be followed until resolution, even if this extends beyond the study-reporting period, which is 4 weeks following the last dose of study product. Resolution of an AE is defined as the return to pretreatment status or stabilization of the condition with the expectation that it will remain chronic.

At any time after completion of the study, if the investigator becomes aware of an SAE that is suspected to be related to study product, the investigator will report the event.

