The selection of 4 months as the duration of antiviral therapy is based upon two findings in the CASG's previous studies of valganciclovir in infants with symptomatic congenital CMV disease who were treated for either six weeks or six months. First, the viral load data from the 6 week versus 6 month study demonstrated the attainment of virologic control by four months of age in the group that received only 6 weeks of antiviral therapy (decrease of whole blood viral load to the level that was seen in the group still receiving treatment) (Figure 2). Second, potential hepatic toxicity was detected after 4 months of treatment in subjects receiving six months of therapy. There was no increased risk of neutropenia among subjects receiving valganciclovir for longer than 6 weeks. Given that the risk of hearing impairment is lower in the asymptomatic congenital CMV population (that is, most babies with asymptomatic congenital CMV infection will not experience hearing loss), we have selected 4 months of treatment to maximize the likelihood of virologic control and minimize the likelihood of adverse effects of therapy (elevated transaminases).

It is critical that this trial be undertaken now. In 2013, the state of Utah passed a law that requires babies who fail their newborn hearing screen to be tested for CMV infection. Other states (Illinois, Connecticut, Tennessee, Texas, New York, and Florida among them) are

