#### 3.2.2 Secondary Outcome Measures

- Cumulative incidence of Grade 3 or higher unsolicited adverse events, safety laboratory adverse events, or serious adverse events
- Cumulative incidence of absolute neutrophil counts below 500/mm^3
- Cumulative incidence of transaminase elevation during treatment  $\geq 2$ -times the baseline value
- Cumulative incidence of adverse events leading to permanent discontinuation of valganciclovir therapy, or any adverse event that is not recovered / not resolved

- 
- Cumulative incidence of sensorineural hearing loss in at least one ear between Baseline and Study Month 4 [both ears with normal hearing at baseline, then at least one ear with sensorineural hearing loss (SNHL) at the 4 month follow-up]
  - Cumulative incidence of sensorineural hearing loss in at least one ear between Baseline and Study Month 12 [both ears with normal hearing at baseline, then at least one ear with sensorineural hearing loss (SNHL) at the 12 month follow-up]
  - Cumulative incidence of sensorineural hearing loss in at least one ear between Baseline and Study Month 18 [both ears with normal hearing at baseline, then at least one ear with sensorineural hearing loss (SNHL) at the 18 month follow-up]
  - Cumulative incidence of each degree of worsened hearing (mild, moderate, severe, profound) at Study Months 4, 6, 12, and 18, represented by the ear that has the larger degree of worsening
  - Proportion of ears of each degree of worsened hearing (mild, moderate, severe, profound) at Study Months 4, 6, 12, and 18

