After obtaining *treatment* informed consent, enrolled subjects will be treated for four months with oral valganciclovir (16 mg/kg/dose, administered two times per day). **Study Day 1** is the day that the first dose of study medication is administered. Audiologic assessments will be made during the Screening Period and Study Months 4 (end of treatment), 6, 12, and 18. A single, independent study audiologist will assess the audiology test battery for each subject and assign each ear the classifications of normal hearing, mild hearing loss, moderate hearing loss, severe hearing loss, or profound hearing loss based upon their hearing thresholds (in decibels). If a study subject proceeds to cochlear implantation during the course of the study, he/she will not require additional study-related hearing assessments following the implantation procedure but will continue with all other study-related assessments.

Treated infants will be followed for safety throughout the first 6 months of the study (including for 2 months post-treatment). Hematology safety laboratory assessments will be obtained weekly for the first six weeks of study drug administration, then every other week for the next six weeks of study drug administration, and then at months 4 and 5. Chemistry safety laboratory

---

assessments will be obtained every other week for the first 12 weeks (3 months) of treatment, and then at months 4, 5, and 6. Adverse events will be assessed at each study visit during treatment, and at month 5.

Whole blood viral load and plasma viral load will be obtained at each study visit during the course of study drug administration, and then at Study Months 5 and 6. Specimens from subjects with increasing viral loads despite antiviral therapy may be evaluated for ganciclovir resistance by molecular methodologies (e.g., deep sequencing, Sanger sequencing, PCR). Urine and saliva will be obtained at Baseline and Study Months 4, 5, and 6 in order to obtain viral isolates to assist in detection of antiviral resistance.

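### Laboratory-AE recording closes 4 weeks after the last dose, so a Grade 3 or higher chemistry value first seen at Month 6 appears to fall outside the safety endpoint

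*Combined protocol and SAP*

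**What the plan says.** Three sections set the same limit on AE recording. Section 9.4 states: "Document all AEs, including safety laboratory AEs, from Study Day 1 through four weeks following the last dose of study drug". It then refers to the "study-reporting period, which is 4 weeks following the last dose of study product". Section 8.1.3 has AEs assessed at visits "continuing through four weeks following the final dose of study drug", and Section 9.2.1 repeats the four-week limit. For serious events Section 9.4 uses a different unit: "Document all SAEs from Study Day 1 through one month after completion of study medication".

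The design section describes a longer period: "Treated infants will be followed for safety throughout the first 6 months of the study (including for 2 months post-treatment". The same section labels Month 4 as the end of treatment and places AE assessment at the treatment visits and at Month 5. Section 8.2.1.2 schedules safety chemistry every other week "for the first 12 weeks (3 months) of treatment, and then at months 4, 5, and 6". The Month 5 visit list (Section 7.3.11) includes an AE review. The Month 6 list (Section 7.3.12) includes ALT, direct bilirubin and creatinine but no AE review.

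The broadest safety outcome in Section 3.2.2 is: "Cumulative incidence of Grade 3 or higher unsolicited adverse events, safety laboratory adverse events, or serious adverse events". It carries no time window. Section 11.4.3 bases the safety evaluation on AEs.

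**The concern.** Blood is drawn from every infant at Month 6 as a safety test, within a period that the design section calls safety follow-up. The rule for what becomes a laboratory AE has closed by then. Because the safety analysis and the Grade 3+ outcome are built on AEs, a new high-grade Month 6 result would have no defined place in the analysis. At stake is whether the reported incidence covers the stated follow-up period or only about half of its post-treatment part. Two statisticians working from this plan could also count the same Month 6 result differently.

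**Working it through.** **Inputs.** Recording limit: 28 days after the last dose (Sections 8.1.3, 9.2.1, 9.4). Last dose: taken as Month 4, since no exact final-dose day is given (Sections 4, 6.2.1). Month 5 and Month 6 visit windows: ±10 days each (Sections 7.3.11, 7.3.12). The length of a study month, m, is not defined. I used 28 days (Section 8.2.1.2 equates 12 weeks with 3 months), 30 days, and the average calendar month of 30.44 days.

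**Step 1: the stated follow-up.** 6 − 4 = 2 months after treatment, which agrees with Section 4. In days this is 2 × 28 = 56 to 2 × 30.44 = 60.9. Recording covers 28/56 = 50% to 28/60.9 = 46% of it.

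**Step 2: Month 6, in days after the last dose.**

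| m | On time (2m) | Earliest (2m − 10) | Latest (2m + 10) | Earliest, last dose 10 days late (2m − 20) |
|---|---|---|---|---|
| 28 | 56 | 46 | 66 | 36 |
| 30 | 60 | 50 | 70 | 40 |
| 30.44 | 60.9 | 50.9 | 70.9 | 40.9 |

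True calendar dates, over every start date in a four-year cycle, give an on-time gap of 59 to 62 days and an earliest visit at day 49. None of the 21 allowed visit days is within 28 days under any definition. Even with the shortest month and the earliest visit, the last dose would have to be 46 − 28 = 18 days late before a Month 6 draw fell inside.

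**Step 3: Month 5, in days after the last dose.**

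| m | On time (m) | Allowed range (m ± 10) | Allowed days within 28 |
|---|---|---|---|
| 28 | 28 | 18 to 38 | 11 of 21 |
| 30 | 30 | 20 to 40 | 9 of 21 |
| 30.44 | 30.4 | 20.4 to 40.4 | 8 of 21 |

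True calendar dates put an on-time visit at day 28 to 31. It is therefore on the limit or up to 3 days past it, and a last dose 3 days late brings it inside (31 − 3 = 28). With the last dose at nominal Month 4, a visit later than its nominal date is outside under every definition.

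**Step 4: early stoppers.** Section 5.3.4 keeps them in follow-up. As an illustration, a last dose on Study Day 42 closes recording on day 42 + 28 = 70. New abnormalities at Day 84 and at Months 4, 5 and 6 are then outside.

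**Step 5: which outcome could count a new Month 6 chemistry value?** Section 3.2.2 lists four safety outcomes.
- Grade 3+ events: worded on AEs, which are closed by then.
- ANC below 500/mm³: worded on counts, but hematology is last drawn at Month 5.
- Transaminase elevation: limited to the treatment period.
- AEs leading to discontinuation or left unresolved: worded on AEs.

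None clearly captures it. Nor need the value be extreme: in Appendix A, after 28 days of age, any direct bilirubin above the upper limit of normal is Grade 3.

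**The case against.** The strongest reply is that being followed for safety is not the same as having AE recording open. The paragraph in Section 4 that gives the 6 months also spells out the content: chemistry to Month 6, AE assessment to Month 5. Month 6 chemistry also has another use, because Section 9.4 has earlier AEs followed to resolution and keeps related SAEs reportable at any time. And the exclusion is inferred, since Section 3.2.2 states no window. All of this is fair. It shows that Month 6 draws are not pointless, but it does not say how a new Month 6 abnormality is to be counted.

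Three stronger readings are tempting, and the documents do not support them.
- A reader might infer that on-time Month 5 results are excluded. AE review is scheduled at that visit, and with four-week months it falls on day 28, inside the limit.
- A reader might turn the Month 5 table into a loss of 10 to 13 of 21 allowed days (48% to 62%). That is a share of days, not of visits, and it fixes the last dose at nominal Month 4.
- A reader might link the gap to the earlier trial's liver signal, where "potential hepatic toxicity was detected after 4 months of treatment in subjects receiving six months of therapy". Those infants were still on drug. Section 2.1 calls the rise slight and not significant, with all means below 90 U per liter; Section 2.3.1 says the laboratory abnormalities were fully reversible on temporary cessation; and Section 2.2 gives the signal as a reason for stopping at 4 months. It is not evidence of toxicity appearing after treatment ends.

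**Conclusion.** The point holds for Month 6. With a last dose at Month 4 or up to 10 days later, every in-window Month 6 chemistry draw lies outside the 28-day limit for every month length tried. A Grade 3 or higher value first seen there is not a laboratory AE. Its omission from the Grade 3+ outcome follows if that outcome counts only recorded AEs, as Section 11.4.3 suggests.

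Month 5 is a secondary matter: an undefined month and a cut-off that falls almost on the visit date. Late in-window visits and early stoppers are the cases affected. The four-week limit for AEs and the one-month limit for SAEs within Section 9.4 also need to be reconciled.

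The size of any under-count is unknown. The documents give no rate of new chemistry abnormalities after treatment, so a claim that late toxicity will be missed would go too far. The change is still worth making, because the data are already being collected.

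**What to change.** - Define a study month in days.
- In Sections 8.1.3, 9.2.1 and 9.4, run AE and SAE recording through the later of one month after the last dose and the Month 5 visit. The words *the later of* are needed: a Month 5 visit 10 days early is only day 18 (28 − 10) to day 20 (30.44 − 10), so the visit alone could shorten the present period.
- Record and grade all protocol-scheduled safety laboratory values through the Month 6 visit.
- In Sections 3.2.2 and 11.4.3, state that the Grade 3+ laboratory outcome counts these values, with on-treatment and post-treatment values shown separately.

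The notification list in Section 9.3.3 and the halting criteria in Section 9.5.2 are also worded on laboratory AEs. The amendment should say whether they take in the later values; that choice is the sponsor's.

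A lesser alternative is to state that Month 6 chemistry is tabulated outside the AE outcome. That removes the ambiguity but leaves a new Month 6 abnormality out of the reported incidence.

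The cost is amendment wording and a few more laboratory AE forms. No new draws are needed. The downside is a slightly higher reported count, which the separate post-treatment display makes interpretable.
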